### **SECONDARY OUTCOMES:**

Secondary outcomes that will be measured are 1) tolerability of the bowel preparation assessed by a patient survey using a modified 5-point Likert scale, 2) percentage of patients requiring a repeat procedure due to unsatisfactory bowel preparation, and 3) percentage of patients receiving rescue medications including magnesium citrate or fleets enemas.

### **METHODOLOGY:**

#### **STUDY DESIGN:**

A randomized, single-center, assessor-blinded trial will be conducted at Cleveland Clinic, a tertiary healthcare center in Ohio, United States. Eligible inpatients at the Cleveland Clinic scheduled for colonoscopy under conscious sedation or general anesthesia will be invited to participate.

Patients eligible for conscious sedation will be randomized at a 1:1:1:1 ratio to receive 1 of the 4 proposed bowel preparation regimens using block randomization. This will be done with a computer-aided system prior to study commencement. The four groups are as follows:

- Group A: 4 Liter PEG-ELS administered as a single day before dose the evening before the colonoscopy,
- Group B: 4 Liter PEG-ELS administered as a split dose the evening before and 4 hours prior to the colonoscopy (currently the standard to which other bowel regimens are compared),
- Group C: SP/MC administered as a single day before dose the afternoon or early evening before the colonoscopy,
- Group D: SP/MC administered as a split dose the afternoon or early evening day before and 4 hours prior to the colonoscopy.

Patients who require general anesthesia will be randomized at a 1:1 ratio to the single, ‘day before dose’ only groups for both PEG-ELS and SP/MC since the anesthesia protocol at our institution mandates strict enforcement of nothing per oral after midnight on the day of the procedure.

- Group E: 4 Liter PEG-ELS administered as a single day before dose the afternoon or early evening before the colonoscopy,
- Group F: SP/MC administered as a single day before dose the afternoon or early evening before the colonoscopy,

- All procedures will be done at the endoscopy suite on the main campus at Cleveland Clinic by a board certified gastroenterologist. The physician and the patients will not be blinded due to major differences in the volume and timing of the bowel cleansing regimens. Primary end-points of this study will be measured between the participants in the all 6groups.

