### **PRIMARY OUTCOMES:**

The primary end-point of this study will be the percentage of in-patients with “satisfactory” bowel cleansing. The efficacy of bowel cleansing will be measured using the Boston Bowel Preparation Scale (BBPS). The BBPS divides the colon into three segments (right, transverse and left) which are scored from 0 to 3 (0= colonic mucosa not seen due to solid stool that cannot be cleared, 1 = only a portion of mucosa of the colon segment is seen due to staining, residual stool and/or opaque liquid, 2= minor amount of residual staining, small fragments of stool and/or opaque liquid, but mucosa of colon segment is seen well and 3 = entire mucosa of colon segment is seen well with no residual staining, small fragments of stool or opaque liquid).

A total BBPS score  $\geq 6$  AND  $\geq 2$  in all segments of the colon will be defined as a “satisfactory bowel preparation”. BBPS scores of  $< 6$  OR  $< 2$  in any segment of the colon will be taken as “unsatisfactory cleansing in the final analysis”.

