#### **PATIENT EDUCATION:**

There is an educational initiative currently underway at Cleveland Clinic to improve the inpatient colonoscopy experience which will also be applicable to all the patients enrolled in our study. The initiative entails:

- 1) Educating the nurses (via educational posters and small didactic sessions),

2) Educating the internal medicine and surgery residents who order the bulk of the inpatient colonoscopies (via educational posters and small didactic sessions),

3) Educating the patients (via detailed instructional pamphlets which will be distributed on the day before the colonoscopy)

Every patient who consents for inclusion in our study will also receive written instructions educating them about the appropriate preparation that needs to be undertaken to make their colonoscopy successful, with special emphasis on proper technique of the bowel cleansing process. Additionally, an investigator or study coordinator would be available to answer any questions that the patient might have related to the bowel purgatory process or the procedure itself.

A clear liquid diet is preferred after awakening the entire day before the procedure. Patients will not be excluded from participating in the study if they have eaten solid food the day before the procedure. Patients will be instructed to consume clear liquids (no solid food) once they begun consuming the bowel preparation until after their colonoscopy. To ensure better comprehension of the patient and success of the bowel cleansing process, the written instructions will specify drinks that qualify as clear liquids. The patient's in each group will be instructed to consume the bowel preparation agent as per their approved FDA labels. Administration of bowel preparations as a split dose is currently the recommendation of choice, for colonic cleansing prior to colonoscopy, in national guidelines (including American Society of Gastrointestinal Endoscopy, American College of Gastroenterology and United States Multi-Society Task Force for colorectal cancer screening).

1) 4 LITER PEG-ELS GROUP (CONSCIOUS SEDATION/SINGLE DOSE DAY BEFORE):

Group A will be instructed to drink the 4-liter PEG-ELS at rates of 8 ounces (240 ml) every 10 min the evening before their colonoscopy and finish drinking the bowel preparation in three hours. They may continue to drink additional clear liquids until 2 hours before their colonoscopy.

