### **ASSESSMENT OF PATIENT TOLERABILITY AND ADVERSE EFFECTS:**

Each patient will be provided a survey at the time of enrollment. The patients will be instructed to complete the survey in “real time” (as they are drinking the preparation). The co-investigator or the study coordinator will collect the survey from the patient prior to receiving sedation for their colonoscopy procedure. The co-investigator or study coordinator will review the survey to ensure all questions are answered.

The purpose of the survey will be to document the following information:

- a. Demographic details (including level of education and annual income),
- b. The start time and end time of the ingestion of bowel cleansing agent,
- c. Total amount of the cleansing agent ingested (to be recorded using a visual depiction of the remaining bowel preparation agent in the container),
- d. Full dose of the bowel cleanser ingested (yes versus no),
- e. Details including the type and timing of symptoms encountered (nausea, vomiting, abdominal pain, bloating, thirst, dizziness, headache or paresthesia),
- f. If any of the above-mentioned symptoms were present prior to the start of the cleansing process, did the use of the purgative agent make them worse (yes versus no),
- g. Ease of use based on a modified 5-point Likert scale: “very easy,” “easy,” “tolerable,” “difficult,” or “very difficult” (score 5–1, respectively),
- h. Palatability based on a modified 5-point Likert scale: “very good,” “good,” “fair,” “bad,” or “worst” (score 5–1, respectively), – *Patients who score ≥3 points in items h) and i) will be classified as the tolerant group.*
- i. Willingness to use the same agent again (yes versus no),

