#### **VARIABLES TO BE STUDIED:**

- Basic demographics: Age, sex, ethnicity, income status, BMI, educational level.
- Pertinent medical history: Comorbidities including history of diabetes, stroke, Parkinson’s disease, hypertension, thyroid disease, constipation, ASA class, opiate use, TCA use, history of IBD, poor preparation in previous colonoscopies (yes/no), Charleston comorbidity index, use of anti-emetics for the bowel cleansing (yes/no).

- Procedure details: Date, indication, bowel preparation quality (reported as BPPS), type of sedation, start time of the procedure, the end time of the procedure, cecal intubation (yes/no), cecal intubation time and withdrawal time.

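### The trial is labelled assessor-blinded, but the physician is stated to be unblinded and no masked scorer of the Boston Bowel Preparation Scale is described, so masking of the primary endpoint is undocumented

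*Combined protocol and SAP*

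**What the plan says.** The combined protocol and SAP opens its Study Design section with "A randomized, single-center, assessor-blinded trial will be conducted at Cleveland Clinic". The same section ends by placing all procedures with a board certified gastroenterologist, and then states: "The physician and the patients will not be blinded due to major differences in the volume and timing of the bowel cleansing regimens".

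Primary Outcomes defines satisfactory cleansing as a total BBPS of at least 6 with at least 2 in every segment. It describes the scoring in the passive voice and names no scorer. A segment score of 1 means "only a portion of mucosa of the colon segment is seen due to staining, residual stool and/or opaque liquid"; a score of 2 requires that the mucosa be seen well despite minor residue. Secondary Outcomes includes the "percentage of patients requiring a repeat procedure due to unsatisfactory bowel preparation".

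Variables to be Studied lists "bowel preparation quality (reported as BPPS" (evidently the BBPS) among the procedure details, next to cecal intubation and withdrawal time. Data Management says that procedure details are taken from the electronic medical record.

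**The concern.** A label of assessor blinding tells readers that the person who scored the primary endpoint did not know the allocation. Here the label and the later statement about the physician appear to conflict, and nothing else in the protocol resolves the conflict.

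The endpoint is one that knowledge of the regimen can influence. Each segment calls for a visual judgement between 1 and 2, and a single segment below 2 makes the whole preparation unsatisfactory. The repeat-procedure outcome uses the same notion of an unsatisfactory preparation, so it is exposed too. The protocol also states its expectations in advance: the Hypothesis section predicts that SP/MC and split dosing will do better, and Patient Education describes split dosing as the choice of national guidelines. A scorer who knows the regimen could lean either way, and a larger sample would not remove such a lean.

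**Working it through.** **1. What the text says about masking.** Every section was read for a scorer and for a masking step.

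| Question | Where to look | What is there |
|---|---|---|
| Is the assessor masked? | Study Design, opening | The label only |
| Who is unmasked? | Study Design, end | The physician and the patients |
| Which physician? | Study Design, preceding sentence | The only one named there is the gastroenterologist doing the procedure |
| Who scores the BBPS? | Primary Outcomes | Not stated |
| How is the score captured? | Variables to be Studied; Data Management | As a procedure detail, from the medical record |
| Second rater, image review, concealment or non-disclosure rule? | All sections | None described |
| Does de-identification help? | Data Management | It covers data handling, analysis and reporting, not scoring during the colonoscopy |

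The only evident scorer, by inference, is the endoscopist.

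**2. Reproducing the plan's sample size.** Inputs from Sample Size Calculation: 50% versus 60%, 95% confidence, 85% power. Two-sided testing is assumed, because the section does not state it. With pooled variance and no continuity correction:

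n per arm = [1.960 × √(2 × 0.55 × 0.45) + 1.036 × √(0.50 × 0.50 + 0.60 × 0.40)]² / 0.10² = (1.379 + 0.726)² / 0.01 ≈ 442.9, so 443 per arm.

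The total is 2 × 443 = 886, which matches the plan. At the planned 1000 patients (250 per group, two groups per agent, so 500 per agent), power is 89.0%.

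**3. What a rating shift would do.** The documents give neither size nor direction, so the shifts below are assumptions. Each is a net change in the proportion of patients rated satisfactory, in one arm only, after the all-segments rule is applied. For n = 500 per arm, with apparent rates p₁ and p₂, d = p₂ − p₁ and p̄ = (p₁ + p₂)/2:

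- SE₀ = √(2p̄(1 − p̄)/n) and SE₁ = √(p₁(1 − p₁)/n + p₂(1 − p₂)/n)
- P(reject) = Φ[(d − 1.96 SE₀)/SE₁] + Φ[(−d − 1.96 SE₀)/SE₁]

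Worked case, true rates 50% in both arms and a 5-point shift: SE₀ = 0.0316, SE₁ = 0.0315, (0.05 − 1.96 × 0.0316)/0.0315 ≈ −0.377, and Φ(−0.377) ≈ 0.353. The other tail is negligible.

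| Assumed shift | Patients of 500 | False-positive rate, true 50% in both arms | Power, planned 50% vs 60%, shift against SP/MC |
|---|---|---|---|
| none | 0 | 5.0% | 89.0% |
| 1 point | 5 | 6.2% (50% vs 51%) | 81.6% (50% vs 59%) |
| 2.5 points | about 12 | 12.4% (50% vs 52.5%) | 66.3% (50% vs 57.5%) |
| 5 points | 25 | 35.3% (50% vs 55%) | 35.3% (50% vs 55%) |

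**The case against.** The best counter-reading is that the unblinded physician is the one who orders the preparation. Patient Education refers to the residents "who order the bulk of the inpatient colonoscopies", so the term could point to them, and the endoscopist could then be the masked assessor. The label and the later sentence would be consistent. This is possible, and it means the protocol does not prove that the scorer is unblinded. It does not rescue the plan: on that reading too, no assessor is named and no step keeps the endoscopist unaware of the regimen.

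A second objection is that the numerical illustration is not evidence about this trial. Any trial of this size would show the same sensitivity to a 5-point shift, and that shift is half the planned effect. The calculation also uses a two-proportion test on the agent contrast, whereas Statistical Analysis plans logistic regression on agent and dose timing. All of this stands. The figures show what is at risk and do not estimate the bias.

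A third is that deleting the label would cure the contradiction but not the rating bias. That is also right, and it is why masking is the preferred remedy and deletion only the fallback.

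**Conclusion.** The concern holds. The claim to assessor blinding is contradicted on the natural reading of Study Design and unsupported on the alternative one. Confidence is high that no scorer and no masking procedure are described; that the scorer is in fact the unblinded endoscopist remains an inference.

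The size of any bias is unknown. If it reached 1 to 5 points in one arm of 500, the false-positive rate would lie between about 6% and 35%, or, with bias against SP/MC, power between about 82% and 35%. These ranges rest on assumed shifts, 500 patients per agent and the planned rates. The sample size calculation itself is not affected. The point must be settled before enrolment, because masking cannot be added once the score has been given during the procedure.

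**What to change.** State in Study Design and Primary Outcomes who scores the BBPS and whether that person is masked. If it is the endoscopist:

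- mask that person to the agent, and to dose timing where possible, until the BBPS has been recorded;
- use a hand-off that does not name the regimen, and ask patients and nurses not to disclose it;
- keep the tolerability survey from the scorer. At present "The co-investigator or the study coordinator will collect the survey from the patient prior to receiving sedation", so the protocol should rule out the scoring endoscopist as collector or reader of it.

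Dose timing cannot be masked under general anesthesia, because Groups E and F both receive a day-before dose. As their timing is the same, this does not bias E against F; it matters only if they are combined with Groups A to D for the single-versus-split comparison.

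If the site cannot do this, remove the assessor-blinded label and report the trial as open-label with unblinded endpoint scoring.

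The cost is protocol wording and a hand-off rule, with no separate reader. The documents do not show how well the regimen can be concealed at this site, and masking will sometimes fail. The fallback costs only wording but leaves the rating bias in place.

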#### **INCLUSION/EXCLUSION CRITERIA:**

All eligible inpatients at Cleveland Clinic older than 18 years of age scheduled for a colonoscopy will be invited to participate in our study. Patients will be excluded if they have/are:

- 1) Creatinine clearance less than 30 ml/min,
- 2) History of heart failure with current shortness of breath at rest causing limited physical activity, arrhythmia, unstable angina ,or acute myocardial infarction,
- 3) Small bowel obstruction, ileus or bowel perforation
- 4) Dementia or cognitive dysfunction to an extent that they cannot perform the study related documentation or consent to participate in the study,
- 5) Gastroparesis,
- 6) Toxic megacolon or undergoing colonoscopy for decompression,
- 7) Taking oral tetracyclines, fluoroquinolones, antibiotics, iron, digoxin, chlorpromazine and penicillamine within 2 hours before or less than 6 hours after administration of CLENPIQ, or stimulant laxatives within 24 hours,
- 8) Allergy to any of the ingredients in CLENPIQ or golytely and/or
- 9) If the procedure is planned in the intensive care unit (ICU).

A member of the study team will identify hospitalized patients who have a colonoscopy procedure scheduled within the next 48 hours. A member of the study team will review the patient's electronic medical record to ensure that the patient is eligible to participate in the study.

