### **BOWEL PREPARATION AGENTS:**

#### **CLENPIQ (SP/MC):**

##### **INDICATIONS/CONTRAINDICATIONS:**

The use of CLENPIQ will be studied in our project and compared to the standard of care which is golytely (4 L PEG-ELS). CLENPIQ is a combination of sodium picosulfate, a stimulant laxative, and magnesium oxide and anhydrous citric acid (SP/MC) which form magnesium citrate, an osmotic laxative, indicated for cleansing of the colon as a preparation for colonoscopy in adults. Contraindications to CLENPIQ use include 1) patients with severely reduced renal function (creatinine clearance less than 30 mL/minute) which may result in accumulation of magnesium, 2) gastrointestinal obstruction or ileus, 3) bowel perforation, 4) toxic colitis or toxic megacolon, 5) gastric retention, and 6) an allergy to any of the ingredients in CLENPIQ.

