### **DRUG INTERACTIONS:**

Use caution when prescribing CLENPIQ for patients with conditions or who are taking medications that increase the risk for fluid and electrolyte disturbances or may increase the risk of renal impairment, seizure, arrhythmias, and prolonged QT in the setting of fluid and electrolyte abnormalities. This includes patients receiving drugs which may be associated with hypokalemia (such as diuretics or corticosteroids, or drugs where hypokalemia is a particular risk, such as cardiac glycosides) or hyponatremia. Use of caution is also advised when CLENPIQ is used in patients with severe active colitis, on nonsteroidal anti-inflammatory drugs (NSAIDS) or drugs known to induce Antidiuretic Hormone Secretion (SIADH), such as tricyclic antidepressants, selective serotonin re-uptake inhibitors, antipsychotic drugs and carbamazepine, as these drugs may increase the risk of water retention and/or electrolyte imbalance.

It is important to note that oral medications administered within one hour of the start of administration of CLENPIQ solution may be flushed from the GI tract and the medication may not be absorbed. Tetracycline and fluoroquinolone antibiotics, iron, digoxin, chlorpromazine, and penicillamine, should be taken at least 2 hours before and not less than 6 hours after administration of CLENPIQ to avoid chelation with magnesium. Prior or concomitant use of antibiotics with CLENPIQ may reduce the efficacy of CLENPIQ as conversion of sodium picosulfate to its active metabolite BHPM is mediated by colonic bacteria.

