### **GOLYTELY (4-LITER PEG-ELS):**

#### **INDICATIONS/CONTRAINDICATIONS:**

GOLYTELY is indicated for bowel cleansing prior to colonoscopy and barium enema X-ray examination in adults. It is contraindicated in patients with gastrointestinal (GI) obstruction, ileus, or gastric retention, bowel perforation, toxic colitis or toxic megacolon or known allergy or hypersensitivity to any component of golytely.

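### The exclusion criteria are narrower than the contraindications the protocol states for both agents, and toxic colitis without megacolon is not excluded at all

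*Combined protocol and SAP*

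**What the plan says.** The section INCLUSION/EXCLUSION CRITERIA lists nine exclusions. Five of them correspond to contraindications of the study agents:

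- Item 1: creatinine clearance below 30 ml/min.
- Item 3: "Small bowel obstruction, ileus or bowel perforation".
- Item 5: "Gastroparesis".
- Item 6: "Toxic megacolon or undergoing colonoscopy for decompression".
- Item 8: "Allergy to any of the ingredients in CLENPIQ or golytely".

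The same section makes this the working rule: a study-team member reviews the "electronic medical record to ensure that the patient is eligible to participate in the study".

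The contraindications themselves are stated later, in the product sections. For CLENPIQ, besides severe renal impairment and allergy, they are "2) gastrointestinal obstruction or ileus, 3) bowel perforation, 4) toxic colitis or toxic megacolon, 5) gastric retention". For GOLYTELY, "It is contraindicated in patients with gastrointestinal (GI) obstruction, ileus, or gastric retention, bowel perforation, toxic colitis or toxic megacolon", with allergy or hypersensitivity added. The CLENPIQ section on drug interactions treats a neighbouring condition more lightly: "Use of caution is also advised when CLENPIQ is used in patients with severe active colitis".

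**The concern.** The protocol describes the same safety limits in two places, and the place used for screening is the narrower one. A screener who follows the exclusion list exactly could pass a patient whom the product sections say should receive neither preparation.

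Randomisation gives no protection, because the affected conditions are contraindications to both agents and every one of the six groups receives one or the other. What is at stake is the safety of individual patients and a protocol that agrees with itself. The sample size, the type I error rate and the primary comparison are not in question.

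**Working it through.** There is no figure to reproduce. The check sets each stated contraindication, counted singly, against the nine exclusion items.

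| Condition | CLENPIQ | GOLYTELY | Exclusion item | Coverage |
|---|---|---|---|---|
| Creatinine clearance below 30 | yes | not listed | 1 | full |
| Ileus | yes | yes | 3 | full |
| Bowel perforation | yes | yes | 3 | full |
| Toxic megacolon | yes | yes | 6 | full |
| Allergy | yes | yes | 8 | full |
| Gastrointestinal obstruction | yes | yes | 3 and 6 | part |
| Gastric retention | yes | yes | 5 | part |
| Toxic colitis | yes | yes | none | none |

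Totals:

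- CLENPIQ: 5 full + 2 part + 1 none = 8 conditions.
- GOLYTELY: 4 full + 2 part + 1 none = 7 conditions.

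The three rows that fall short are these:

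1. **Toxic colitis.** Both product sections name it alongside toxic megacolon. Item 6 keeps only the megacolon. No other item names toxic colitis.
2. **Obstruction.** The product sections put no limit on the site. Item 3 limits it to the small bowel. Item 6 removes an obstructed colon only when the colonoscopy is for decompression. Large-bowel obstruction examined for another reason, and gastric outlet obstruction, are not named.
3. **Gastric retention.** Item 5 names gastroparesis. Retention from another cause is not named.

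Nothing else in the documents closes the gap:

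- Item 8 names both products but concerns allergy only, and no item refers to contraindications in general.
- Item 9 excludes procedures planned in the ICU. That removes some very ill patients, but by location and not by diagnosis.
- PATIENT EDUCATION refers to the approved labels, but about how patients take the preparation, not about who may enter.
- The exclusion section does not refer the screener to the product sections.

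The list also reads as if it were complete. Item 1 repeats the renal limit from the CLENPIQ contraindications, and item 7 takes up the interaction timing from the CLENPIQ drug-interaction section. A screener would have little reason to look further.

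**The case against.** The strongest reply is that the contraindications are in the protocol, stated in full for both products, so this is a drafting mismatch within one short document. Candidates are inpatients already scheduled for colonoscopy, and 4 L PEG-ELS is the site's standard of care. The documents do not show that enrolment would expose anyone to a purgative they would otherwise have avoided. Clinicians would probably catch many such patients. This limits how heavily the point should weigh, but it does not remove it: the screening rule does not require the catch.

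Three narrower objections have some force:

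- **The count depends on how conditions are split.** CLENPIQ's contraindications are numbered 1 to 6. On that numbering, three (1, 3, 6) are fully covered, three (2, 4, 5) partly, and none is wholly uncovered. Toxic colitis appears as uncovered because it is counted apart from toxic megacolon. For GOLYTELY, allergy and hypersensitivity are counted as one condition; a stricter reader could call that row partial too. The same three gaps remain on any of these counts.
- **Obstruction and gastric retention are secondary.** Each is partly covered, and what remains depends on a strict reading. Toxic colitis is the main gap.
- **Severe active colitis is only a caution for CLENPIQ.** Keeping such patients eligible agrees with the protocol's own product text and is not a fault. Adding the term toxic colitis would not define the line between severe and toxic. It would, however, tell the screener that there is a line to draw, which the present list does not do.

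**Conclusion.** The concern holds. The exclusion list falls short of the protocol's own contraindications on three conditions, identically for both agents and therefore in all six groups. Toxic colitis without megacolon is wholly missing; obstruction and gastric retention are partly covered.

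The conclusion rests on reading the exclusion list literally and as the rule for eligibility, which is how its section presents it. How many patients would fall in the gap cannot be estimated, because the documents give no frequency for any of the three conditions. The point should be corrected on safety grounds. It implies no change to the endpoint, randomisation, sample size or analysis.

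**What to change.** Either of two changes is enough:

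- Merge and reword items 3, 5 and 6, for example: *obstruction at any level of the gastrointestinal tract; ileus; bowel perforation; gastric retention, including gastroparesis; toxic colitis; toxic megacolon; colonoscopy for decompression.*
- Or add one item for all six groups: *any contraindication to CLENPIQ or GOLYTELY.*

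The first is easier to apply at screening because it names the conditions. The second is shorter and also settles the allergy and hypersensitivity wording. A brief working definition of toxic as opposed to severe colitis would help the screener with either.

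The cost is one to three lines of protocol wording and a few more screen failures, in patients who by the protocol's own account should receive neither agent.
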